13.3 Accrual and Feasibility

We expect to screen 300 potential participants to randomize 180 women, 60 per arm. We assume the drop-out rate to be 10%. Our goal is to achieve a total sample size of 162 evaluable participants (54 participants per arm).

13.4 Primary Objective, Endpoint(s), Analysis Plan

Primary objective and primary endpoint

Since the primary objective of this study is to assess if the reduction in estradiol with the standard dose is comparable with the other lower doses, we will measure the estradiol before and after treatment. Thus, the primary endpoint is the percentage change of serum estradiol concentration from baseline and we will compare the median change and percentage changes among arms.

We choose the percentage change as the primary endpoint because it will improve generalization of results, given the wide variability among different assays, and because we predict that a large percentage of participants will have the final values of estradiol below the detectable level.

Analysis plan

We will present full distribution and median values of estradiol at baseline (before treatment), at post (after treatment), and changes and percentage changes (with interquartile ranges) of estradiol level, from baseline to post, by arms. Differences by arms of % change, change and final values will be tested considering t-test and ANCOVA models. Estradiol at baseline will be included as explanatory variable together with other possible confounders such as BMI, age and time since last dose. Normal distribution of residuals from full model will be checked and, if needed, a transformation will be considered.

We will also compare percentages of participants with final values of estradiol below the detectable level by arms with Chi-square tests and logistic models.

We will carry out the two comparisons with the standard dose considering $\alpha=0.025$.

Power analysis

Given the expected reduction of at least 80% change with exemestane at 25 mg daily (56) considered as reference group (control arm) against 25 mg 3 times a week, or 25 mg weekly, for the power calculation we assume a non-inferiority difference of 6% in percentage changes of estradiol after treatment from baseline, using a one-sided, two-sample t-test. A total sample size of 162 participants (54 participants per arm), enables us to achieve 80% power with a margin of equivalence of -6% in the mean percentage changes from baseline at the lower dose compared to the standard dose. The true difference between the means percentage changes is assumed to be 0.0%.

The significance level of the test is 0.025 to take into account of multiple comparisons (we will compare the changes at the two low doses with the standard dose)(57).

The data are drawn from populations with common standard deviations of 11% (58).

Assuming a 10% drop-out rate while on study, we would need to randomize 180 participants (60 participants per arm) to achieve the total sample size of 162 evaluable participants (54 participants per arm).

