9.1 Rationale for Methodology Selection

Estradiol

Serum estradiol concentrations will be determined by use of a CLIA certified test, according to MD Anderson policies for primary endpoint analyses. This test is based on a non-derivatized LC-MS/MS technology that has a detection limit of 2 pg/ml, a limit that may not be sufficient to detect estradiol levels in all postmenopausal women. Any samples that have estradiol results below the detection limit will be assigned to have a concentration of ½ the value of the detection limit.

Because of the critical issue of sensitivity of the method, we have decided to include an additional validated bioanalytical method performed in a CLIA certified laboratory for steroid testing. Estradiol will be measured by a two-dimensional liquid chromatography with mass spectrometry detection LC-MS/MS) after liquid-liquid extraction. Duplicate standard curves, water blanks and four assay control pools are processed with samples to assess accuracy and precision of the assay. This method has a lower detection limit (1 pg/ml) than the CLIA certified estradiol test (Quest) and will serve as a quality control since it has proven to more effectively detect estradiol concentrations at the very low level, characteristic of older postmenopausal women. The functional sensitivity of the test is 1 pg/ml and the within assay precision of two control samples were 13% at 1.0 pg/mL and 8.8% at 5 pg/mL, respectively.

Ki-67

Ki-67 labeling index modulation in preoperative studies has proven to be an appropriate surrogate marker for outcome in participants who are administered antiestrogen therapies.

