13.6 Reporting and Exclusions

The primary analysis will employ an intention-to-treat approach, which includes all women irrespective of compliance. An according-to-protocol subgroup analysis will be restricted to women who are “compliant”, such as participants who have taken $\geq 80\%$ of the active scheduled pills, and notably, due to the different arm schedule, $\geq 80\%$ of the active pills has to be reached also in the last 7 days before surgery.

Due to limitations of estradiol analysis procedures, small concentrations cannot be precisely measured. These concentrations are said to be below the limit of detection (LOD). We will consider a statistical method that uses the characteristics of the distribution of the values above the LOD to estimate the values below the LOD. This can be done with an extrapolation technique or maximum likelihood estimation that has smaller error rates than all the standard replacement techniques (Methods of Dealing with Values Below the Limit of Detection using SAS. Croghan et al.).

Patterns of observations for covariates will be classified as complete cases (no missingness), terminal (monotone) dropouts, intermittent (non-monotone) dropouts, mixed and no-data. Kendall’s τ_b will be computed in order to test the correlation between a dichotomous indicator of missing observations and treatment assigned as well as any possible baseline covariates.

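### Undetectable baseline estradiol has no agreed handling: under section 9.1's half-limit rule a woman undetectable before and after scores 0% change, and a few such women would cut the stated 80% power

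*Combined protocol and SAP*

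**What the plan says.** - **Endpoint (13.4):** "the primary endpoint is the percentage change of serum estradiol concentration from baseline".
- **Sizing (13.4):** the daily arm is expected to show a reduction of at least 80%. The test is specified "using a one-sided, two-sample t-test", "with a margin of equivalence of -6% in the mean percentage changes from baseline", with 54 evaluable women per arm. "The true difference between the means percentage changes is assumed to be 0.0" (percent). "The significance level of the test is 0.025 to take into account of multiple comparisons". "The data are drawn from populations with common standard deviations of 11" (percent).
- **Low values, first rule (9.1, Estradiol):** the primary assay detects down to 2 pg/ml, and the section concedes that this may miss some postmenopausal women. "Any samples that have estradiol results below the detection limit will be assigned to have a concentration of" half that limit. The rule is not confined to post-treatment samples.
- **Low values, second rule (13.6):** estimation from the distribution above the limit, by extrapolation or maximum likelihood, will be considered. It is described as more accurate than replacement.
- **Who is analysed:** sections 4.1 and 4.2 contain no estradiol criterion. Section 13.6 says: "The primary analysis will employ an intention-to-treat approach, which includes all women irrespective of compliance". Section 13.8 likewise has no exclusion on baseline estradiol. Section 13.4 anticipates many undetectable final values but does not mention undetectable baselines.

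**The concern.** A percentage change needs a measured denominator. When baseline is below the limit, half-limit replacement supplies a constant instead. If the final value is also below the limit, the score is (1 − 1)/1 = 0%. If the final value is exactly 2 pg/ml, the score is (2 − 1)/1 = +100%. Neither number reflects what the drug did.

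In a trial sized on a mean near −80% with SD 11, such a score lies about seven SDs from the rest. It inflates the variance of a comparison whose margin is only 6 points. If such women fall unevenly between arms, it also shifts the estimated difference. The trial could then miss non-inferiority, or appear to show it, because of women whose result carries no information on the schedules.

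**Working it through.** **Inputs from section 13.4:** margin 6 points, SD 11, true difference 0, one-sided 0.025, 54 per arm, reference mean −80%. **From section 9.1:** limit 2 pg/ml, replacement value 1 pg/ml. **Assumed:** the number of women undetectable both before and after treatment, because the documents give no baseline distribution.

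**1. The plan's own figure.** SE = 11 × √(2/54) = 2.12, and 6/2.12 = 2.83. Power from the noncentral t with 106 df is 80.2%. The stated 80% is reproduced.

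**2. Exactly one woman per arm at 0%, the other 53 at N(−80, 11).** Expected sample variance = [52 × 121 + (53/54) × (80² + 121/53)]/53 = 237.3, so SD = 15.4. SE = 15.4 × √(2/54) = 2.96, and 6/2.96 = 2.02. Power is 51.8% by noncentral t and 52% by simulation of the t-test. Restoring 80% would take 104 per arm.

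**3. A random number per arm (simulation, both arms at the same rate).**

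| Assumed share at 0% | Expected women per arm of 54 | Power |
|---|---|---|
| 0 | 0 | 80% |
| 0.1% | 0.05 | 78% |
| 0.5% | 0.27 | 72% |
| 1% | 0.54 | 64% |
| 2% | 1.08 | 53% |
| 5% | 2.7 | 34% |

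**4. Imbalance.** Each such woman moves her arm's mean by 80/54 = 1.5 points, a quarter of the 6-point margin. With one in a low-frequency arm only, power is 39%. With one in the daily arm only, it is 87%. In that second case, if the true deficit equals the margin, non-inferiority is declared in about 4.5% of trials instead of 2.5%. These figures are conditional on the imbalance having occurred.

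**5. Baseline adjustment.** With one such woman per arm, ANCOVA on baseline (assumed median 5 to 12 pg/ml, geometric SD 1.7) gives 52% to 59%. A separate indicator for an undetectable baseline, which the plan does not include, gives 79%.

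**6. Leaving these women out.** Power under SD 11 is 79.4% with 53 per arm, 78.7% with 52 and 77.9% with 51.

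**7. A check without fixing the other women at −80%.** Here baselines are assumed lognormal, the true fall is about 88%, and every value below 2 pg/ml is scored 1.

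| Assumed baseline median, log-SD | Below 2 pg/ml | Power, all women | Power, measurable baseline only |
|---|---|---|---|
| 6.8 pg/ml, 0.4 | 0.1% | 97% | 99.5% |
| 6.8 pg/ml, 0.6 | 2% | 60% | 93% |
| 5 pg/ml, 0.4 | 1% | 78% | 97% |
| 5 pg/ml, 0.6 | 6% | 32% | 84% |

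The loss ranges from slight to severe. The restriction raises power in every scenario.

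**The case against.** **The half-limit rule may not govern.** A reader might infer that an undetectable baseline scores 0% whatever the drug does. The documents do not support that. Section 13.6 speaks of low concentrations generally, and under its method both values would be estimated, so 0% is not forced. Even under section 9.1 the score is +100% if the final value is 2 pg/ml. This stands, and it limits the point to the half-limit rule. It does not remove the point: section 13.6 only says the method will be considered, section 9.1 states a definite rule, and under either one the denominator is not measured.

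**The share is unknown and may be tiny.** This also stands. At 0.1% there is about a 90% chance (0.999^108) of no such woman in the two arms compared, and little power is lost. Excluding BMI below 18.5 and capping BMI below 25 at half of each site's women should make low baselines less common. A reader might also take the figures for exactly two or three women in each arm, 29% and 15%, as the likely loss. Those need equal counts in both arms; the same rates varying at random give about 41% and 32%.

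**SD 11 may already include such women.** This is unlikely. One woman at 0% among 54 contributes 80²/54 = 118.5 of the 121 units of variance.

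**Section 13.4 has other analyses.** It plans medians, absolute change, final values, the proportion undetectable and a possible transformation, and the 1 pg/ml assay is a secondary endpoint. All of these help interpretation. None is the powered comparison, and no margin is set on another scale.

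**An entry criterion was not practical.** Agreed. Baseline blood is drawn before randomisation but stored and assayed later (sections 3 and 10.3). The remedy therefore belongs in the analysis.

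**Conclusion.** The concern holds in a conditional form. A stated rule scores a woman undetectable before and after treatment as 0%, nothing in entry or analysis deals with her, and sections 9.1 and 13.6 disagree on how low values are treated. If the half-limit rule governs and the other women follow the stated design, power falls from 80% to between 78% and 34% for assumed shares of 0.1% to 5%, and to about 52% with exactly one per arm. Chance imbalance moves an arm mean by about 1.5 points per woman.

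The documents do not show that the trial will lose its power, because the share of such women is not given. What they do show is that the primary result may depend on a few scores, under a rule that has not been settled. This should be resolved before the data are unblinded.

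**What to change.** Reconcile sections 9.1 and 13.6 by naming one rule for values below the limit in the primary analysis. State in 13.4 and 13.6 that the primary percent-change comparison is made in randomised women whose baseline sample is at or above the primary assay's limit. That sample is drawn before randomisation, so the restriction does not depend on treatment even though the assay comes later. Report the other women separately by arm. Add an all-randomised sensitivity analysis, and use the already planned 1 pg/ml assay as support.

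The cost is protocol wording and a few women leaving the primary comparison, about 1 to 3 points of power under the stated SD. The primary result would then apply to women with measurable baseline estradiol and would no longer cover everyone randomised. The restriction does not remove the ceiling for baselines between 2 and 5 pg/ml. With undetectable final values scored as 1 pg/ml, the largest recordable fall is 1 − 1/baseline: 50% from 2 pg/ml, 75% from 4 and 80% only from 5.

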Arm 2: Exemestane 25 mg/ 3 times a week (3 active tablets and 4 placebo tablets)

Arm 3: Exemestane 25 mg/once a week (1 active tablet and 6 placebo tablets)

Treatment start (day 1)

The participant starts treatment, a telephone contact will be performed only if different from the randomization day

Telephone contact (a week before surgery +3 days)

Review of self-reported compliance, concomitant medications, toxicity assessment.

Final clinical visit (the day of surgery or the day before)

Physical exam, toxicity assessment, concomitant medications, blood collection for clinical lab tests and circulating biomarkers, compliance/review pill diary. The blood withdrawn for biomarkers will be at 12 hours, 1.5-2.5 days and 5.5-6.5 days from last active dose respectively for arm 1, 2 and 3 depending on scheduled final visit. Participants continue intervention until the night before surgery

Surgery (4 to 6 weeks; ideally at day 29)

Surgery performed; Surgical specimens collected

* After identifying the pool of 180 potentially eligible women with ER-positive in-situ or invasive breast cancer, women in Italy and the U.S. undergo identical procedures. Specifically, consent for blood draw, laboratory testing, completion of questionnaire, etc. -as outlined under baseline clinic visit- will be performed.

Endpoints

Primary endpoint: Percentage change in time of serum estradiol concentration at alternative dosing schedules compared to daily dose.

Secondary endpoints: Safety and toxicity, change in Ki-67 and PgR expression, tissue estradiol, exemestane and 17-dihydroxyexemestane concentration.

Circulating estrogens (including ultrasensitive estradiol measurement), androgens and sex hormone binding globulin, exemestane and 17-dihydroxyexemestane, adipokines, glucose, insulin and lipid profile. Further secondary endpoints will be proteomics and UGT2B17 genotype and measurement of crown-like structures in non-cancerous breast fat tissue.

TABLE OF CONTENTS

COVER PAGE.....	1
SCHEMA.....	7
1. OBJECTIVES.....	10
1.1 Primary Objective.....	10
1.2 Secondary Objectives.....	10
2. BACKGROUND.....	10
2.1 Breast Cancer.....	10
2.2 Exemestane.....	10
2.3 Rationale.....	11
3. SUMMARY OF STUDY PLAN.....	14
4. PARTICIPANT SELECTION.....	15
4.1 Inclusion Criteria.....	15
4.2 Exclusion Criteria.....	15
4.3 Inclusion of Women and Minorities.....	16
4.4 Recruitment and Retention Plan.....	16
5. AGENT ADMINISTRATION.....	16
5.1 Dose Regimen and Dose Groups.....	16

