13.8 Evaluation of Response

All participants included in the study who have taken at least one dose of study agent will be assessed for response to study treatment even if there are major protocol deviations or if they are ineligible. All of the participants who met the eligibility criteria (with the possible exception of those who did not receive study agent) will be included in the main analysis. All conclusions regarding efficacy will be based on all eligible participants.

All randomized participants who received at least one dose will be included in the study analysis with an intent-to-treat approach. A secondary analysis will also be carried out after excluding non-compliers and participants who will drop-out and who will refuse treatment after randomization. Using a more conservative approach, participants who drop-out will be considered in the failure group. Both the intent-to-treat and efficacy analyses will be conducted on a per-participant basis.

Reasons for excluding participants from the analysis will be clearly reported and sub analyses may not serve as the basis for drawing conclusions concerning efficacy. For all measurements of response, the 95% confidence intervals will also be provided.

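### Section 13.4 sizes the trial on a one-sided 6-point non-inferiority test, but its analysis plan tests only for differences and ties no confidence limit to the margin

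*Combined protocol and SAP*

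**What the plan says.** Sections 1.1, 3 and 13.1 call this a non-inferiority trial, and section 1.1 asks for the comparison to be adjusted for baseline estradiol.

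The power analysis in 13.4 is specific. It assumes a "non-inferiority difference of 6% in percentage changes of estradiol after treatment from baseline, using a one-sided, two-sample t-test", states the margin as a "margin of equivalence of -6% in the mean percentage changes from baseline at the lower dose compared to the standard dose", and takes significance level 0.025, SD 11, true difference 0 and 54 evaluable women per arm. The reference is an "expected reduction of at least 80% change with exemestane at 25 mg daily".

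The other parts of 13.4 are looser. The endpoint paragraph names percentage change as primary and adds that "we will compare the median change and percentage changes among arms". The analysis plan says "Differences by arms of % change, change and final values will be tested considering t-test and ANCOVA models". Baseline estradiol goes in as a covariate, with "other possible confounders such as BMI, age and time since last dose". A transformation may be used. The two comparisons with the daily dose are made at 0.025, with no sidedness given.

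Section 13.8 adds: "For all measurements of response, the 95% confidence intervals will also be provided". It does not relate those intervals to the margin.

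**The concern.** A non-inferiority conclusion needs a confidence limit, or an equivalent shifted test, set against the margin. A test of difference has a different null hypothesis, and failing to reject it does not show that the deficit is under 6 points. The margin appears only where the sample size is justified, so the plan does not say what result would make a schedule non-inferior.

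Three details widen the gap:

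- Two model types are considered on three outcomes, with an open covariate list. None is called primary.
- The margin is signed, but the coding of percentage change is not given. With an 80% reduction on daily dosing and 74% on a reduced schedule, the difference is 74 − 80 = −6 on the percent-reduction scale and −74 − (−80) = +6 on the signed-change scale. Worse is negative on one and positive on the other.
- Time since last dose is not defined. The Schema puts the final blood draw at "12 hours, 1.5-2.5 days and 5.5-6.5 days from last active dose respectively for arm 1, 2 and 3". If the covariate means last active dose, it is separated by arm when tablets are taken as scheduled.

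At stake is the trial's one primary conclusion, for two schedules.

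**Working it through.** **Inputs, all from 13.4:** margin 6 points, SD 11, n = 54 per arm, one-sided 0.025, true difference 0.

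**1. The plan's own figure.** SE = 11 × √(2/54) = 2.117. Noncentrality = 6 / 2.117 = 2.834 on 106 degrees of freedom. Power of the one-sided 0.025 t-test is 80.2%, and 54 is the smallest n per arm that reaches 80%. With 10% drop-out, 54 / 0.9 = 60 per arm, or 180 in all. The stated size reproduces.

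**2. When the margin test passes.** t(0.975, 106) = 1.983, so the half-width of the two-sided 95% interval is 1.983 × 2.117 = 4.20. Non-inferiority requires observed deficit + 4.20 < 6, so the observed deficit must be below 1.80 points.

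**3. When a difference test is non-significant.**
- One-sided 0.025 or two-sided 0.05: deficit up to 4.20 points.
- Two-sided 0.025: t(0.9875, 106) = 2.274, and 2.274 × 2.117 = 4.81 points.

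Observed deficits from 1.8 to 4.2 points (or 4.8) are therefore not significantly different and also fail the margin.

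**4. Error rate if non-significance were taken as success.** For a schedule truly 6 points worse (noncentral t, noncentrality 2.834):

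| Rule | Chance of passing |
|---|---|
| 95% limit excludes 6 points | 2.5% |
| Not significant, two-sided 0.05 or one-sided 0.025 | 19.8% |
| Not significant, two-sided 0.025 | 28.8% |

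**5. Reading of 0.025.** If it were applied as a two-sided 97.5% interval against the margin, power at 54 per arm would be 71.2%, not 80.2%.

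**6. Time since last dose, only if it means last active dose.** Assume doses are taken as scheduled, arm 1 is sampled at 0.5 days, and a share p of women is sampled at the later end of the Schema window in arms 2 and 3 (1.5 or 2.5 days; 5.5 or 6.5 days). The documents do not give p, so it is varied from 0.1 to 0.9.

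The slope on time is then estimated only from the one-day spread within arms 2 and 3:
- slope SE = 11 / √(54 × 2p(1 − p))
- mean time gap from daily = 1 + p days (three times weekly) or 5 + p days (weekly)
- adjusted SE = √(2.117² + (gap × slope SE)²)

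At p = 0.5 the slope SE is 2.117. The adjusted SE is √(2.117² + (1.5 × 2.117)²) = 3.82 for three times weekly and √(2.117² + (5.5 × 2.117)²) = 11.83 for weekly. Power falls to 35% and 7%. Over p = 0.1 to 0.9 it is 13% to 37% and 5% to 7%. If the term means last tablet, taken nightly in every arm (5.2) and recorded as last pill intake (7.5), there is no such loss.

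**The case against.** The strongest reply is that the analysis plan and power analysis are adjacent parts of one section and should be read together. Both use a t-test, 0.025, percentage change and two comparisons with the daily arm. The margin and sidedness stand in the power analysis, and the 95% interval in 13.8 is numerically the one a one-sided 0.025 margin test needs. On this view only a linking sentence is missing. That is fair as to the size of the repair, but that sentence is the decision rule, and the paragraph governing the analysis describes a different test.

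Several stronger readings are tempting, and the documents do not support them:

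- *The plan treats non-significance as non-inferiority.* It does not say so. The 20% and 29% figures show what that reading would cost.
- *No model is indicated.* Section 1.1 asks for baseline adjustment and 13.4 includes baseline estradiol, which an unadjusted t-test cannot do. A baseline-adjusted ANCOVA is strongly implied. It is not named as primary, and the remaining covariates are open.
- *The primary test is on medians and is underpowered.* The endpoint paragraph speaks of comparing medians, but the analysis plan only presents them with interquartile ranges. The named tests are mean-based and no median test is planned.
- *The margin's sign is wrong.* The power analysis speaks of a reduction, and on that scale −6 means worse. The scale only needs stating.
- *The time covariate will ruin the analysis.* That holds only under the active-dose reading. It is one item in a list of possible confounders, and the size of the loss depends on assumed sampling times.

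**Conclusion.** The point stands as a missing decision rule, not as a sample-size error. A declared non-inferiority trial has an analysis plan that tests differences, with no interval tied to its 6-point margin and no model named as primary. At the planned size, observed deficits between 1.8 and 4.2 points (4.8 at two-sided 0.025) would be non-significant yet fail the margin test, so the conclusion would depend on a rule chosen later. These figures rest on the plan's own SD of 11, 54 evaluable women per arm and an unadjusted t-test. Adjusting for time since last active dose would remove most of the power of the arm comparison when doses are taken as scheduled. That part is conditional on an undefined term. The rule should be settled before any comparison by arm is made.

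**What to change.** Amend 13.4 to state:

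- **Primary analysis.** ANCOVA of mean percentage change on arm, baseline estradiol, centre and BMI stratum. The last two are the stratification factors in 13.2.
- **Decision rule.** A schedule is non-inferior if the upper limit of the two-sided 95% interval (one-sided 0.025 per comparison) for reduced minus daily signed percentage change is below +6 points. Equivalently, the lower limit is above −6 on the percent-reduction scale. Say which scale is used.
- **Supportive analyses.** Label the t-test, median summaries, absolute change and final values as such.
- **Time since last dose.** Define it. Keep time since last active dose out of the primary model and report it within arm.
- **Transformation.** If it remains an option, state in advance what the margin becomes on the transformed scale.

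The cost is a wording amendment, through the approvals in 14.3, and 4 degrees of freedom for five centres. The sample size is unchanged: 80.2% power at 54 per arm.
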